## **Background of research**

Colorectal Cancer is the commonest cancer diagnosed for both genders combined in Hong Kong. In 2015 16.6% of all new cancer cases registered on the Hong Kong registry were cancer of colon and rectum. Distal colon cancer is more common than proximal colon cancer, with up to 38% of cancers being found in the rectum. Curative surgical treatment option for rectal cancer involves excision of tumour with 5cm proximal and 2cm distal margin with its draining lymphatics. The level of anastomosis or need for temporary or permanent stoma will depend on the height of tumour from the anal verge, extent of local invasion, the sphincter function preoperatively, co-morbidity and whether they required preoperative chemoradiotherapy. With neoadjuvant chemoradiotherapy offering potential tumour shrinkage and improvements in surgical technique such as the transanal total mesorectal excision (TaTME) technique offering accurate distal resection margin, many patients are now receiving sphincter-preserving surgery with low colorectal or coloanal anastomosis to avoid permanent colostomy. Up to 80% of patients who has undergone low anterior resection (LAR) suffer from severe bowel dysfunction post operatively. Patients symptoms typically fall into two categories: those with incontinence, frequency, and urgency, and those with constipation and feelings of incomplete emptying. However, some patients report features of both, either occurring simultaneously or fluctuating between these two groups of symptoms. This combination of symptoms after LAR is referred to as Low Anterior Resection Syndrome (LARS) which is associated with negative impact on quality of life (QoL). Originally, it was thought that these symptoms were short-lived neorectal irritability in the postoperative period. However, many studies report that the majority (up to 90%) of patients experience long-term changes in quality of life after LAR^6. Therefore, a large number of patients worldwide are suffering from unpredictable, poor bowel function postoperatively affecting their day-to-day activity and quality of life.

In a prospective study assessing consecutive patient's functional outcome post low anterior resection in our unit since January 2016, 34 patients have had their defunctioning stoma closed to date with 4 months follow up. 73.5% of our patients were experiencing major LARS. Approximately half of the patients had persistent symptoms at 2 years post stoma closure: 65.5% (19/29) and 46.2% (6/13) had major LARS at 12 and 24 months respectively. Hence, the figures from our unit correspond to reports from other centers Worldwide.

Unfortunately, there is no cure for LARS at present. Biofeedback treatment and nerve stimulation sacral nerve stimulation or tibial nerve stimulations with stimulators such as the Acutens seems to provide some symptomatic relief for some patients. The cause of LARS is thought to be multifactorial and difficult to define. Therefore, this trial is designed to use Fecobionics, a new Hong Kong based innovation, to provide new mechanistic insights regarding anorectal physiological function post low anterior resection. This will help us to understand the condition better and hopefully to improve their treatment options.

## **Technological background**

In the proposed studies it is important to compare the new technology, Fecobionics, to current state-of-the-art reference technologies. We expect Fecobionics to provide data that cannot be obtained with current technology and to reduce variation in measured variables.

### **Reference testing techniques**

**Anorectal Manometry (ARM) with balloon expulsion testing (BET)** will be conducted with a standard single-use 8ch anorectal catheter (G-90150, MMS, Enschede, Netherlands). The catheter will be inserted with the subjects lying inside position with bent hip and knees. The bag will be placed in the rectum and pressure will be measured at 0.5cm distance in the anal canal. The following parameters will be evaluated: resting anal pressure, maximum anal squeeze pressure, the recto-anal inhibitory reflex (RAIR), urge volume, maximum tolerable volume, and expulsion time for the 50ml balloon.

**Defecography (fluoroscopy or MRI)** will be used as a reference for Fecobionics. A water-soluble paste will be injected into the rectum and serial x-rays will be taken during defecation. Defecography will be used to study several anorectal characteristics. The height of the colorectal anastomosis, any abnormality at the anastomosis such as narrowing, orientation of neo-rectum will be assessed in addition to usual measurements of the anorectal angle and the position of the pelvic floor at rest or during Valsalva (perineal descent). The presence of rectocele, rectal intussusception, and the ability to expel rectal contents will be evaluated. Balloon proctography can simplify the procedure of examining the ability to evacuate by providing a quick and clean test with minimal radiation.

### **New technology**

**Fecobionics** is a novel device, a simulated faeces, that we currently are testing in healthy subjects and in patients suffering from fecal incontinence and constipation (RGC funded proposal “Unraveling anorectal function and biomarker signatures in patients suffering from subtypes of defecatory disorders”). Fecobionics records pressures, orientation, bending, shape, and viscoelastic properties during defecation. It is made of a 10 cm long and 12 mm wide core of medical grade resin that contains multiple electronic sensors and circuit boards. A bag is mounted on the bendable core. Pressure transducers are placed at the front, rear and inside the bag, in addition to two gyroscopes for orientation and angle measurements. A novelty of Fecobionics is that it measures pressures in axial direction (in the direction of flow) in contrast to current technologies and that it integrates almost all current anorectal functional tests into a single test that only takes minutes to perform without the use of radiation or expensive equipment. Since the Fecobionics technology was developed by the PI [name], we are currently the only clinical research group with access to the technology. This gives us a unique opportunity to become the leaders in the field.

### **Impact**

Defecatory disorders affect 25% of the population with rising incidence. They pose a major health care

burden and are poorly recognized and treated. The need for better diagnostics and therapeutics is substantial. Constipation, a symptom of underlying disease, affects 12-19% of Americans with expenditures on medication for constipation alone greater than \$250 million per year. Defecatory diseases are associated with diet, aging and a variety of underlying factors and diseases. As described above LAR is associated with reduced quality of life and anorectal symptoms in the majority of patients.

Since the etiology is multifactorial, a significant problem is the lack of physiologically relevant and practical diagnostic tests for identifying the underlying mechanisms. Assessment begins with detailed questioning about symptoms. Digital rectal examination is done to assess tone, maximum anal squeeze with detection of sphincter defects, rectal prolapse, and abnormal perineal descent. Current diagnostic tests such as Anorectal Manometry (ARM), Balloon Expulsion Test (BET) and defecography are surrogates for the act of defecation and provide incomplete and often conflicting information due to the static nature of the tests. Not surprisingly results of these tests correlate poorly with symptoms and treatment outcomes. The problem with most tests is that they do not reflect the dynamics of the defecation process and are far from representing physiological conditions. Even defecography, regarded as the most physiological test, uses a liquid with mechanical properties quite different from the properties of faeces. The anorectal expulsion test suffers from the lack of physiological measurements such as pressure profiles, angling and geometric changes during anal passage. Hence, current paradigms for defecatory disorders need to be changed by approaches that can provide insight by simulating defecation physiologically and examining the mechanistic changes multidimensionally in terms of pressure profiles, deformability, and topographic changes. Based on promising new data using the Functional Luminal Imaging Probe (FLIP) in the anal canal, ARM, and Fecobionics, the goal is to use the novel integrated Fecobionics device (combined FLIP-ARM-BET-defecography-in-part) for functional studies in LAR patients. Fecobionics has been developed according to current safety standards for medical devices (ISO13485) by the PI [name] and have been trialed with success in our patients with anorectal functional disorders based on GRF support. We are currently the only clinical research centre worldwide with access to the technology. This provides us with a unique opportunity to lead the field. The measurement variables include pressures, shape changes, the expulsion velocity and an “objective” anorectal angle (important for evaluation of several anorectal disorders). Hence, it will be feasible to describe objectively, without disturbing the defecation process, sensation, opening characteristics and geometric changes during initial entry from the neo-rectum into the relaxing anal canal.

This proposal will result in a new paradigm in evaluation of LARS. The simulated faeces technology will potentially replace current tests as it provides an integration of measurements from multiple tests of anorectal diagnostics. Our expected outcome is to characterize abnormal pressures, forces and topographic changes in the neo-rectum and anal canal during defecation in LARS patients, to help with understanding of the cause of their symptoms to guide and improve LARS management.

## Objectives and specific aims

### General Objective

Fecobionic will provide new mechanistic insights regarding anorectal physiology in LARS patients that is not obtainable with current technology.

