### Data collection:

Patients will be assessed at baseline and following will be recorded for all patients:

- Demographic data
- Body Mass Index (BMI)
- Significant Past Medical and Surgical History
- Obstetric History (female patients only)
- Rectal Cancer stage: TNM staging, location of tumour from anal verge on preop image

- Rectal Cancer treatment
  - o Neoadjuvant chemoradiotherapy/radiotherapy/chemotherapy
  - o Surgery – Open/Laparoscopic/Robotic/TaTME, level of anastomosis
  - o Post-operative complications
  - o Postop chemotherapy / radiotherapy
  - o Timing of defunctioning stoma (ileostomy / colostomy) closure
- LARS questionnaires: to assess Quality of life associated with LARS (Figure 4)

All patients will undergo the following tests:

- Integrated Fecobionics anorectal test (see clinical workflow below)
- High Resolution Anorectal Manometry (ARM) to assess resting and squeeze pressures, sensitivity, rectal capacity and recto-anal inhibitory reflex.
- Conventional balloon expulsion test
- Defaecography

Clinical data will be recorded and stored electronically in the hospital server. Completed questionnaires will be recorded and entered into database software and stored in the hospital server.

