**Exclusion Criteria:**

1. Patients who are not willing to undergo the specified tests in this study
2. Pregnant women

The studies on LARS patients will focus on pathophysiological studies where we describe the expulsion characteristics, with focus on anal canal opening related to rectal mechanosensory data and to changes in the anorectal angle during defaecation. We will study expulsions at the urge-to-defecate level for the patients and we will correlate to data obtained by conventional technologies and to patient characteristics such as age, and symptoms as well as to risk factors. The study subjects will also be tested with conventional expulsion testing, defecography, rectal bag distension, and ARM. The studies will determine endpoints of clinical value such as expulsion time and velocity, maximum angle difference, pressure signatures and geometry changes.

**Expected Results and Milestones:** The expected outcome is that the device will perform as shown in the previous human experiments (n>60) where no adverse effects have been recorded. We anticipate successful access in LARS patients with no device-related adverse events or device malfunctions. Completion of the study is expected to derive outcome measures reflecting the defecatory function as the major impact.

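### The planned correlations and between-method ANOVA cannot show whether Fecobionics explains symptoms beyond the conventional tests, or agrees with them on shared measures, although every patient has the paired data

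*Combined protocol and SAP*

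**What the plan says.** The General Objective is "new mechanistic insights regarding anorectal physiology in LARS patients that is not obtainable with current technology". Technological background gives the same expectation, "We expect Fecobionics to provide data that cannot be obtained with current technology and to reduce variation in measured variables", and states that "it is important to compare the new technology, Fecobionics, to current state-of-the-art reference technologies".

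Under Data collection, "All patients will undergo the following tests" introduces a list of Fecobionics, high-resolution ARM, conventional BET and defecography. Reference testing techniques says of defecography that it "will be used as a reference for Fecobionics".

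The planned analyses that bear on the comparison are:

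- **Specific Aim 1:** regression, named as the primary tool, to associate symptoms with experimental findings. No model is written out.
- **Aim 1 study design (text after the exclusion criteria):** "we will correlate to data obtained by conventional technologies".
- **Data analysis section:** ANOVA and single or multiple regression on differences between two methods, with methods and variables unnamed, and a coefficient of variation for repeatability.
- **Sample-size text in that section:** limits of agreement, computed on preliminary expulsion times from BET and Fecobionics to help set n. They are not listed as an analysis of the trial data.

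The Impact section adds: "The simulated faeces technology will potentially replace current tests".

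**The concern.** The objective sets Fecobionics against current technology, and the primary analysis is about symptoms. A reader of the final report will therefore want to know whether a Fecobionics variable says something about symptoms that ARM, BET and defecography do not.

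The device is described in the Approach section as integrating those tests, so overlap is built in. A significant association between a Fecobionics variable and the LARS score could be a second measurement of urge volume or expulsion time. The plan has no step that would reveal this. The study could then report new insight into symptoms when the evidence shows only that the device reproduces a known relation.

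Agreement has the same gap. If the results are later used to discuss replacing tests, neither a correlation nor a test of mean difference shows that two methods give interchangeable readings in a patient.

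**Working it through.** **1. What each planned analysis can show**

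| Planned analysis | What it shows | Beyond conventional tests? | Agreement? |
|---|---|---|---|
| Correlation with conventional tests | Strength of linear relation | No | No: a constant or proportional bias leaves r high |
| ANOVA on differences between methods | Mean difference | No | No: a zero mean difference can hide wide individual differences |
| Regression of symptoms on findings, model not stated | Association with symptoms | Only if conventional measures are in the same model | No |
| Coefficient of variation | Spread relative to the mean | No | No |

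**2. The plan's own figure**

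The document's formula is n > [(1.96 + 0.84) × σ/δ]². Neither δ nor σ is given, so n = 30 cannot be reproduced. Solving backwards, δ/σ = 2.80/√30 = 0.51. This is a standardised mean difference and does not speak to added explanatory value.

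**3. What a nested comparison could detect with n = 30**

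The documents name no model, so these inputs are assumptions: p = 2 or 3 conventional predictors, u = 1 added Fecobionics predictor, two-sided alpha 0.05 and 80% power.

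- Error degrees of freedom: v = 30 − p − u − 1 = 26 (p = 2) or 25 (p = 3).
- Test: F(1, v) for the added term, with f² = partial R²/(1 − partial R²).
- Two conventions for the noncentrality parameter are in use: f² × n, and f² × (u + v + 1). Both are shown.

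| Noncentrality | p | f² for 80% power | Partial R² | Power at true partial R² = 0.10 |
|---|---|---|---|---|
| f² × 30 | 2 | 0.282 | 0.22 | 42% |
| f² × 30 | 3 | 0.283 | 0.22 | 42% |
| f² × 28 | 2 | 0.303 | 0.23 | 40% |
| f² × 27 | 3 | 0.315 | 0.24 | 38% |

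If the conventional measures alone reached R² = 0.30 (an assumption), the detectable increase in R² would be 0.70 × 0.22 = 0.15 to 0.70 × 0.24 = 0.17. With p = 3 and the second convention, 80% power at a true partial R² of 0.10 needs about 76 patients.

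Adding more Fecobionics variables costs power. With p = 3 and the second convention, the detectable partial R² rises to 0.32 for three added variables and 0.38 for five. This is why one named variable is preferable.

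**4. Precision of an agreement analysis with n = 30**

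With s the SD of the paired differences, each 95% limit of agreement has an approximate 95% CI of ±1.96 × √(3/30) × s = ±0.62 s (±0.65 s in a t-based form). That is wide but reportable.

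**The case against.** The strongest reply is that the objective is about measurement, not prediction. The protocol uses the idea of data that current tests cannot give for quantities such as axial pressure, bending and geometry during passage. The Aim 1 milestone is descriptive, and the sample-size text calls the study exploratory and concedes that it may be too small for confounders. A variable can be new and mechanistically informative without raising R-squared for a symptom score. This stands: novelty of the measured variables needs no statistical test. It does not cover the step from new variables to explaining symptoms. Aim 1 makes symptom association the primary analysis, and the Impact section looks to understanding the cause of symptoms and guiding management.

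Two stronger readings are tempting, and the documents support neither:

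- **A reader might infer that replacing current tests is a stated objective that goes untested.** The General Objective does not mention replacement. It appears as a hedged expectation in the Impact section, argued from the integration of several measurements in one device.
- **A reader might infer that no planned analysis compares the methods.** Correlations and between-method ANOVA or regression are planned, and the unspecified multiple regression does not exclude conventional covariates. The fault is that these analyses, as written, do not answer the two questions.

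It is also fair that a nested model with 30 patients will often be inconclusive. That argues for presenting it as an estimate with an interval, not for omitting it.

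**Conclusion.** The point holds in this limited form. The plan collects what is needed to judge added explanatory value and agreement, but specifies no analysis that does so. It is a gap between objective and analysis that should be closed. It does not invalidate the descriptive work.

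With 30 patients, only a substantial gain is detectable with 80% power: a partial R-squared of about 0.22 to 0.24. This rests on two or three base predictors, one added predictor, complete data in all 30 patients and the usual linear-model assumptions. None of these is fixed by the documents. Change in R-squared bears on added value only and cannot support a statement about replacement, which needs agreement on shared measures.

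**What to change.** Before analysis, add two items to the Data analysis section.

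1. **Added explanatory value (exploratory).** For the LARS score, the only symptom score that the protocol names, fit (a) a model with two or three named conventional measures, for example resting pressure, urge volume and BET time, and (b) the same model plus one named Fecobionics measure. Report the change in R-squared with a bootstrap 95% CI. This change cannot fall below zero in the sample: with no true gain, the expected partial R-squared is already 1/27 to 1/26, about 0.04. Report the added coefficient with its CI alongside, and do not read a lower bound above zero as proof.

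2. **Agreement.** For expulsion time (Fecobionics against BET) and anorectal angle (Fecobionics against defecography), replace the ANOVA and correlation comparison with Bland-Altman limits of agreement and their CIs, the method already used for sizing. State in advance how failed expulsions enter. Note that BET uses a 50 ml balloon whereas Fecobionics is filled to urge, so wide limits may partly reflect filling.

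Base any claim of added explanatory value on item 1, and any statement about potential replacement on item 2. Report smaller gains as unproven.

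Cost: no extra patients, tests or visits, only a short addition to the plan and some analysis time. The price is that the conclusion may be less favourable than the protocol expects.

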### Specific Aim 1: Anorectal pathophysiology of LARS patients

Objective: use fecobionics to obtain physiological and pathophysiological signatures of anorectal function in a heterogeneous group of LARS patients. Based on the epidemiology and symptomatology of LARS, it is expected that the heterogeneous group will contain an almost equal number of LARS patients with incontinence, frequency and urgency, and those primarily with constipation and feelings of incomplete emptying. Due to the spread (heterogeneity) in the patient group regarding symptoms, regression analysis will be the primary statistical tool to associate symptoms with experimental findings. We will also compare to age- and sex-matched healthy controls from already conducted studies.

Milestone: Describe the mechanosensory signature, variation of the measured variables, and computed endpoints in LARS patients.

## Approach

**Device Characteristics and human recordings.** The integrated Fecobionics device is uniquely designed to improve diagnostics of anorectal disorders. The design integrates ARM, BET, defecography and FLIP. The new design features of the integrated device are shown in Figure 1 and include the inner bendable core that contains the sensors and a bag for distension made of 25 micrometer polyurethane. The core is easily bendable and contains electronic components such as pressure transducers, gyroscopes, and impedance electrodes as well as circuit boards for the central processing unit (CPU). A tube is used for filling of the bag after the placement in rectum to the urge-to-defecate level. All materials in the device are medical grade. The core and the bag provide a double layer protection for the electronic components. Our institutional review board did not have any concerns about the risks and safety of the device.

**Figure 1** shows the design of the Fecobionics device with the computer that also serves as a visual analog scale (VAS) for sensory evaluation in addition to displaying data. The core is made from medical grade resins and contains three pressure sensors placed at the front, rear and inside the bag. It also contains two gyroscopes used for determination of orientation and bending (the anorectal angle). Furthermore, eight pairs of electrodes that utilizes the FLIP principle to determine the geometry of the bag surround the core. The core also contains the CPU, multiplexer, amplifiers, and batteries. A valve and bag filling tube system as well as a safety thread are attached in the front of the device (not shown).

**Figure 2** shows schematics of novel analysis of the pressure signals from preliminary studies in healthy human subjects and patients with anorectal disorders. The left panel shows the front and rear pressure and the difference between them as function of time. Studies have demonstrated that defecation can be subdivided into five distinct phases. The difference in the two axial pressures (pointing forward and

backward) during the expulsion indicate the usefulness of this kind of measurements. For example, the entrance of the device into the canal as well as the anal relaxation can be assessed. The right panel shows the front pressure as function of the rear pressure. This is a novel representation corresponding to the well-known preload-afterload analysis of cardiac function. Human data from our preliminary data are shown in figure 3.

**Figure 3** shows data from a healthy subject (AB), a patient with fecal incontinence (CD) and chronic constipation (EF). The left panels are the pressure-time plots useful subdividing defecations into phases. The right panel is the front-pressure as function of the rear pressure. Both types of analysis show marked differences between the subjects. In general, the healthy subjects use a few pressure increases (abdominal contractions) to expel the device. The FI subject is characterized by a low anal sphincter pressure and the device pops out by itself. The constipation patient cannot expel the device despite many attempts. Other data (not shown) based on gyroscope data also demonstrate distinct differences between subjects.

